## Data collection

1. Identify domains (e.g. provinces, districts) to be included in the study. Factors to consider include: (i) capturing a range of transmission strata, (ii) ensuring broad geographical representation, and (iii) optionally, weighting based on population at risk.
2. Select 10 health facilities per domain for testing (if this is not possible, a smaller number of health facilities may be viable; see Table 2 for variations in the number of health facilities and recommended sample numbers). Any facility in which RDTs are being used is eligible; microscopy services are not a requirement. Selection of health facilities may be through randomization or deliberate choice (e.g. sentinel surveillance), and must ensure balanced representation of the target population.
3. In the target population (suspected malaria cases), conduct routine case management procedures and obtain informed consent (or assent, depending on the age of majority and federal guidelines in the country of enrolment) to perform an additional RDT and collect at least two dried blood spots (DBSs) for laboratory analysis and for biobanking/long-term storage to support future malaria epidemiological and diagnostic research.
4. Take clinical history, including questions regarding age, sex, recent malaria diagnostic testing, antimalarial therapy and travel.
5. Test all consenting suspected malaria cases simultaneously using both a WHO-recommended HRP2 RDT and a non-HRP2-based method (e.g. Pf-LDH RDT (separate single or multiple test line RDT)) or quality-assured microscopy in the health facility, and collect a minimum of two DBSs on filter paper or protein saver cards.
6. Record demographic and clinical history details and all test results on the survey report form.
7. Administer antimalarial therapy based on results from (either) RDT and/or microscopy, according to national guidelines.
8. Retain used RDTs for quality control and a minimum of two DBSs from all consenting *P. falciparum* patients for molecular +/- serological analysis.
9. Enrolment can stop once 30 individuals with confirmed *P. falciparum* malaria from each of 10 health facilities have been recorded in the survey tally sheet as having *P. falciparum* (a different number of confirmed individuals is required per health facility if using other than 10 clusters; see Table 2).
10. Ship all consent forms, tally sheets, survey report forms and patient samples to the central coordinating centre.

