or below the limit of detection of the HRP2 and Pf-LDH RDTs. In addition, there are several situations in which this indicator could miss a true *pfhrp2/3* gene deletion (see Table 1). First, individuals will not be detected if they have a low-density infection that is missed by Pf-LDH RDT or microscopy and also missed by HRP2 RDT because of *pfhrp2/3* gene deletion. Second, HRP2 RDTs may still detect some infections with a *pfhrp2* deletion due to cross-reactivity of test antibodies with HRP3. Finally, the testing protocol will not detect *pfhrp2/3* deletions in patients coinfecting with HRP2-expressing clones, unless certain techniques are used, such as quantitative PCR (22–24), deep sequencing (25,26) and digital PCR (27). For these reasons, this indicator represents the lower limit of the true prevalence of *pfhrp2/3* gene deletions but should detect all clinically significant *pfhrp2/3* deletions.

**Table 1. Summary of test result combinations and limitations of the approach, including only individuals with discordant HRP2 RDT results (positive by Pf-LDH or microscopy AND negative by HRP2 RDT)**

HRP2 RDT	Pf-LDH RDT or microscopy	Molecular analysis performed a	Interpretation of results and limitations in detecting pfhrp2/3 deletions
+	+	No	
 
• May be infection with pfhrp2 deletions but HRP3 was detected by HRP2 RDT
 
• May be multiclonal infection with parasites with and without pfhrp2/3 deletions
 

+	-	No	
 
• False-positive HRP2 RDT (or persisting HRP2 after resolution of infection)
 
• May be infection with pfhrp2 deletions but HRP3 was detected by HRP2 RDT, or may be multiclonal infection with parasites with and without pfhrp2/3 deletions
 
 
and
 
 
• Low parasite density at or below the limit of detection of Pf-LDH RDTs and/or microscopy
 

-	+	Yes	
 
• False-positive Pf-LDH RDT or microscopy
 
• Low parasite density at limit of detection of RDTs (variable reactivity of test lines)
 

-	-	No	
 
• Cannot exclude low-density infection missed by both RDTs and microscopy, with undetected pfhrp2/3 deletions
 

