**Table 4. Available non-WHO-prequalified tests meeting critical criteriaa**

Product name	Product code	Manufacturer name
Biocredit Malaria Ag Pf (pLDH)	C14RHG25, C14RHH25	Rapigen Inc.
Biocredit Malaria Ag Pf (pLDH/HRP2)	C13RHG25, C13RHH25	Rapigen Inc.
Biocredit Malaria Ag Pf/Pv (pLDH/pLDH)	C61RHG25, C61RHH25	Rapigen Inc.
CareStart™ Malaria Pf (HRP2/pLDH) Ag RDT	RMPM-02571	Access Bio Inc.
CareStart™ Malaria PAN (pLDH) Ag RDT	RMNM-02571	Access Bio Inc.

a Valid ISO 13485:2003, submission of application for WHO prequalification, and acceptable diagnostic performance against both HRP2-expressing and non-HRP2-expressing at 200 parasites/μL (*pfhrp2/3* single or double deletions), based on the most recent WHO laboratory assessment performed at the United States Centers for Disease Control and Prevention.

- For each consenting suspected malaria case, the health provider will attach a unique survey ID, chronologically ordered, to a survey case report form (Annex 7) and to the survey tally sheet (Annex 6). On the survey case report form, the health worker will record answers to questions regarding age, sex, and recent history of malaria diagnostic testing, treatment and travel.
  - Next, using the labels attached to the survey case report form (with the same ID number as the form), the health worker (treating clinician or laboratory worker) will label two different RDTs or one RDT and microscopy slide and a filter paper or protein saver card for DBS. The health worker will perform the tests, record the results on the survey case report form (Annex 7, sections 5–7), and either inform the patient of the results directly (clinician) or refer (laboratory worker) the patient back to the treating clinician for treatment in the case of positive test results on the primary or secondary RDT, or microscopy as per national guidelines. Results from either RDT should be acted upon, as both are WHO-prequalified. Microscopy is also considered an acceptable alternative to malaria RDTs. Negative RDT results should be managed as per national guidelines.
3. All used RDTs and, if applicable, microscopy slides from each consenting suspected malaria case will be stored until the survey is complete in a dry and protected area for survey quality control purposes.

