  - Molecular-based confirmation of *pfhrp2/3* deletions is needed to ensure that discordant results are caused by *pfhrp2/3* gene deletions and not by other factors, such as operator error, false-positive Pf-LDH test lines, false-positive microscopy results, or samples at the limit of detection of the RDTs, which may not always react sufficiently to generate a positive test line. The contribution of these alternative causes of discordant results will vary.
  - Serological confirmation of *pfhrp2/3* gene deletions may also be performed using immunoassays, especially on samples where there is lack of agreement between RDT and PCR results.
8. Once the true number of cases with false-negative HRP2 RDT results caused by *pfhrp2* gene deletions is known, the prevalence at the domain level can be calculated for each sampling domain (e.g. province, state), using the DRpower software or interactive web app (<https://shiny.dide.ic.ac.uk/DRpower-app/>). This software also calculates a 95% CrI around this estimate (see Annex 3). The raw calculation is based on the formula:

$$\text{Proportion of } P. \text{ falciparum} \text{ cases with false-negative HRP2 RDT results due to } pfhrp2/3 \text{ deletions} = \frac{\text{\# of confirmed } P. \text{ falciparum} \text{ cases with } pfhrp2/3 \text{ gene deletions and HRP2-RDT negative results}}{\text{\# of confirmed } P. \text{ falciparum} \text{ cases (positive by either Pf-LDH RDT or microscopy)}}$$

9. Statistical analysis in DRpower will also result in an estimate of the probability that the prevalence of false-negative HRP2 RDT results caused by *pfhrp2/3* gene deletions is above 5%. This will result in one of two outcomes per domain:

**Outcome 1:** The posterior probability of being above the 5% threshold is less than 0.95. In this case, there is not sufficient evidence to conclude that the proportion of false-negative RDT results caused by *pfhrp2/3* gene deletions among symptomatic *P. falciparum* patients is greater than 5%.

**Outcome 2:** The posterior probability of being above the 5% threshold is greater than or equal to 0.95. In this case, there is high statistical confidence that the proportion of false-negative HRP2 RDT results caused by *pfhrp2/3* gene deletions among symptomatic *P. falciparum* patients is greater than 5%.

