**Table A1.1. Supplemental DBS analysis options and associated limitations in detecting *pfhrp2/3* gene deletions**

HRP2 RDT	Pf-LDH/microscopy	Diagnosis	Order of priority for DBS analysis	Interpretation of results and limitations in detecting pfhrp2/3 deletions
+	+	P. falciparum	2	
 
• May be infection with pfhrp2 deletions but HRP3 was detected by HRP2 RDT
 
• May be multiclonal infection with parasites with and without pfhrp2/3 deletions
 

+	-	P. falciparum	3	
 
• False-positive HRP2 RDT (or persisting HRP2 after resolution of infection)
 
• May be infection with pfhrp2 deletions but HRP3 was detected by HRP2 RDT
 
• May be a low-density P. falciparum infection that does not result in Pf-LDH reaction with RDT due to low antigen concentration
 
• May be multiclonal infection with parasites with and without pfhrp2/3 deletions
 

-	+	P. falciparum	1	
 
• False-positive Pf-LDH RDT or microscopy
 
• Low parasite density at limit of detection of RDTs causing variable RDT reactivity
 

-	-	Negative for malaria	4	
 
• Cannot exclude low-density infection missed by both RDTs, with undetected pfhrp2/3 deletions. Use PCR to exclude malaria infection.
 

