## Annex 6. *pfhrp2/3* gene deletion survey facility tally sheet

This sheet will be filled out by all facilities. In each domain, once 300 individuals with *P. falciparum* malaria have been seen (30 at each of 10 enrolment sites per domain), calculate the proportion of discordant diagnoses (i.e. Pf-LDH- or microscopy-positive AND HRP2 RDT-negative) among all positive *P. falciparum* diagnoses, i.e. by Pf-LDH RDT or microscopy. When centrally compiled, section 5.6 points 6 and 8 can be used to interpret the results and determine the associated actions after statistical analysis of the molecular +/- serological confirmation data.

A	B	C	D	E	F	G
Patient ID	Date of visit / test (DD/MM/YY)	Informed consent/ assent	Pf case confirmed by Pf-LDH RDT/ microscopy	Cumulative number of consenting Pf positive cases (from column E)	Suspected false-neg HRP2 (Pf-LDH or microscopy positive AND HRP2 RDT negative)	
1		Y / N	Y / N/ NA		Y / N/ NA	
2		Y / N	Y / N/ NA		Y / N/ NA	
3		Y / N	Y / N/ NA		Y / N/ NA	
4		Y / N	Y / N/ NA		Y / N/ NA	
5		Y / N	Y / N/ NA		Y / N/ NA	

\* Expand rows as needed

Total suspected malaria cases tested (column A) \_\_\_\_\_

Tally total of *P. falciparum* cases detected and enrolled per facility (column F equals total confirmed *P. falciparum* cases enrolled).

Number of suspected false-negative HRP2 RDT results (column G – sum of “yes” responses) **(a)**

Total number of positive *P. falciparum* diagnoses by Pf-LDH RDT or microscopy (it is important to establish which method will be used for counting Pf cases before the study is undertaken, as this is an important criteria for defining the total number of Pf cases enrolled in the study) (last entry column F) **(b)**

Percentage of all *P. falciparum* cases with suspected false-negative HRP2 RDT results that need molecular +/- serological analysis for *pfhrp2/3* deletions = **(a / b)**

Target: 30 *P. falciparum* cases detected and enrolled per facility (last entry column F)

1 This number may vary according to overall sample size of the survey and the number of clusters selected.

[figure not shown]
[figure not shown]

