### To be completed prior to participant interview

1.	Barcode/patient ID	Place label									
2.	Health centre	Pre-entered for each health centre on printed form or combined with survey ID									
3.	Name of health worker/lab assistant										
4.	Date of visit	Day _____ Month _____ Year _____									
5.	Pre-entered for each health centre on printed form:  RDT 1 (must include HRP2 – national programme RDT)	 
 
 	Box 1	
 
 Control	Pf HRP2	
 
 + / -	+ / -	
 
 
Circle correct result in each box above.
 
Circle result of RDT:      1. Negative    2. P. falciparum
		Box 1	Control	Pf HRP2	+ / -	+ / -			
	Box 1										
Control	Pf HRP2										
+ / -	+ / -										
6.	RDT 2 (survey RDT)  a. Name: b. Product code: c. Lot number: d. Expiry date: e. Target antigens: 1. T1: 2. T2: 3. T3:	 
 
 	Box 2	
 
 Control	T2 Pf-LDH	T1 HRP2	
 
 + / -	+ / -	+ / -	
 
 
Circle correct result in each box above.
 
Circle result of RDT:      1. Negative    2. P. falciparum
		Box 2		Control	T2 Pf-LDH	T1 HRP2	+ / -	+ / -	+ / -
	Box 2										
Control	T2 Pf-LDH	T1 HRP2									
+ / -	+ / -	+ / -									
7.	a. Is RDT 1 positive for P. falciparum ? b. Is RDT 2 positive for P. falciparum ?	Y / N Y / N If YES to EITHER question, provide treatment.									

8.	DBS taken?	a. Y / N b. Consent for long term storage Y/N																				

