**FOR SUPERVISOR USE ONLY**

S1	a. Is box 1 negative?	Y / N
	b. Is box 2 positive?	Y / N

If YES to part a and part b, the result is discordant.

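### Where RDT 2 is a combination HRP2/pLDH test, the case definition lets a patient positive only on its HRP2 line be counted as a confirmed case, which would lower the prevalence compared with 5%

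*Protocol*

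**What the plan says.** **Case count and denominators.** The Annex 6 column that fills the 30-case target is headed "Pf case confirmed by Pf-LDH RDT/ microscopy". The step 8 formula in section 5.6, repeated in section 5.10, divides by confirmed "cases (positive by either Pf-LDH RDT or microscopy"). The step 6 formula and Annex 8 footnotes b and c also name the test and not the line. Under step 9 of Data collection in the project summary, a facility may stop enrolling at 30 such cases.

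**Which test this may be.** Step 5 of Data collection allows a "Pf-LDH RDT (separate single or multiple test line RDT"). Two of the five products in Table 4 combine the two antigens, for example "CareStart™ Malaria Pf (HRP2/pLDH) Ag RDT". The example form in Annex 7 prints RDT 2 with both a Pf-LDH and an HRP2 line.

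**How the result is summarised.** Box 2 of the form records each line. The summaries are for the whole test: item 6 asks for negative or *P. falciparum*, and item 7 asks "b. Is RDT 2 positive for" *P. falciparum*.

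**What is expected and meant.** Table 1 has a row for HRP2-positive, Pf-LDH-negative patients, explained among other causes as "False-positive HRP2 RDT (or persisting HRP2 after resolution of infection"). Table A1.1 adds low-density "infection that does not result in Pf-LDH reaction with RDT due to low antigen concentration", yet its diagnosis column for that row reads *P. falciparum*. Table 1, the definition of a discordant result in Annex 6 and the footnote to section 5.2 all treat Pf-LDH as a line or antigen result.

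**The concern.** A patient whose combination RDT 2 shows only the HRP2 line belongs to the HRP2-positive, Pf-LDH-negative row of Table 1. The output formulas appear meant to leave that row out. Read literally, though, the patient is positive by the device that defines a confirmed case, and a health worker could tick the tally column.

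This patient has HRP2 reactivity on RDT 2 and is usually positive on RDT 1 too. The output 1 numerator requires a negative HRP2 RDT, so the patient would almost never enter it. Two things follow: the denominator grows without the numerator, and the facility stops before it has 30 cases positive on the Pf-LDH line or by microscopy.

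The error runs in one direction, towards Outcome 1. Under section 5.6, Outcome 1 in all domains leads to a repeat survey, while Outcome 2 in any domain leads to a nationwide change of RDT. Domains that use different RDT 2 products would also stop being comparable.

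Correcting the supervisor check S1 ("b. Is box 2 positive"?) would not cure this. These patients are mostly RDT 1 positive, so they fail the first part of S1 and still sit in the quota and the denominator.

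**Working it through.** **Inputs from the protocol.** 10 facilities × 30 = 300 cases; true prevalence 10% for power; power 80% (section 5.4, Table 2). Outcome 2 requires Pr(p > 5%) ≥ 0.95 (section 5.4). ICC r = 0.05 for Table 2; priors p uniform on [0, 1] and r ~ Beta(1, 9) (Annex 3).

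**Assumed input.** f is the share of counted cases positive only on the HRP2 line of RDT 2. The documents do not give it. The range used is 5% to 30%, taken as equal across facilities.

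**Step 1: reproduce the plan's power.** Facility prevalence is drawn from Beta(α, β), with α = 0.10 × (1/0.05 − 1) = 1.9 and β = 0.90 × 19 = 17.1. Counts are binomial, and the posterior is computed on a (p, r) grid. With 3,000 to 4,000 simulated surveys per setting:

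| Design | Power at true 10% |
|---|---|
| 10 × 30 | 81% (second run 82%) |
| 9 × 37 | 81% |
| 8 × 51 | 82% |
| 7 × 68 | 80% |
| 6 × 113 | 80% |

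Table 2 reproduces for these five designs.

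**Step 2: dilution if the error stays in the denominator.** Counted cases per facility remain 30, but only a share 1 − f can be in the numerator:

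- apparent prevalence = p × (1 − f)
- true prevalence that reads as 5% = 0.05 / (1 − f)
- facility counts ~ Binomial(30, xᵢ(1 − f)), where xᵢ is the facility prevalence among the cases that are meant to be counted

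| f | True 10% reads as | True value reading as 5% | Chance of Outcome 2 at true 10% |
|---|---|---|---|
| 0 | 10% | 5.0% | 81–82% |
| 5% | 9.5% | 5.3% | 77% |
| 10% | 9.0% | 5.6% | 71–72% |
| 20% | 8.0% | 6.3% | 56% |
| 30% | 7.0% | 7.1% | 38–39% |

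Ranges reflect separate simulation runs. At a true 8%, with 20,000 surveys per setting, the chance of Outcome 2 falls from 53% to 40%, 27% and 15% for f = 10%, 20% and 30%.

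**Step 3: the denominator is rebuilt from Box 2.** Only the quota shortfall remains. Valid cases per facility are 30 × (1 − f) = 27, 24 and 21 for f = 10%, 20% and 30%. Two separate runs gave power at a true 10% of 79%, 79%, 76% and of 82%, 80%, 77%. At a true 8%, one run gave 54%, 52% and 51%, against 55% at f = 0.

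So most of the loss in Step 2 comes from the denominator and little from stopping early.

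**The case against.** The strongest reply is that this is a loose label and not a wrong definition. Table 1 uses a negative Pf-LDH RDT to mean a negative Pf-LDH line. The section 5.2 footnote requires Pf-LDH-specific lines, section 5.6 speaks of false-positive Pf-LDH test lines, and Annex 6 defines discordance by Pf-LDH positivity. Box 2 keeps the lines apart and prints only the Pf-LDH heading in bold. Annex 7 is an example that may be adapted to the RDTs used, and the supervisor reviews the RDT results centrally. The denominator can therefore be built correctly from data already collected.

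Much of this stands: the intent is the Pf-LDH line, and a central rebuild would remove most of the harm. What does not stand is that the matter is already settled. The footnote rules out pan-pLDH lines, not an added HRP2 line. Annex 6 asks for the counting method to be fixed beforehand, but this does not fix the line. No passage instructs anyone to rebuild the denominator.

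A reader might infer three stronger things that the documents do not support:

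- **That the protocol makes these patients confirmed cases.** It leaves the point open. No passage fills the tally column from item 7, whose stated purpose is treatment.
- **That they can never be in the numerator.** A patient negative on RDT 1 but positive on RDT 2's HRP2 line could be flagged at S1 if Box 2 is read as a whole, and then be confirmed by molecular testing. Almost never is the defensible wording.
- **That the survey will lose power on the scale of Step 2.** Those figures need an assumed f and an error that survives into the final analysis.

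**Conclusion.** The concern holds as an ambiguity with a one-sided consequence. Where RDT 2 is a combination test and is read as a whole, the wording allows patients positive only on its HRP2 line to count towards the quota and the denominator, against the evident intent. The bias is towards Outcome 1.

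The size is conditional. For assumed f of 10%, 20% or 30%, with the error left in the final denominator, a true 10% reads as 9%, 8% or 7%, and the chance of Outcome 2 falls from about 81% to about 71%, 56% or 38%. This is the worst case for each f. If the denominator is rebuilt from the recorded lines, the chance stays at about 76–82%. At sites using microscopy or a Pf-LDH-only test, f is zero and nothing changes.

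The change is worth making because it protects the 5% decision and costs almost nothing.

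**What to change.** - In the Annex 6 column and totals, the step 6 and step 8 formulas of section 5.6, the section 5.10 formulas and Annex 8 footnotes b and c, state that a confirmed case is one positive on the Pf-LDH test line or by microscopy, and that an HRP2 line on the same test does not count.
- Add one item to Annex 7, such as: Pf-LDH line of RDT 2 positive? Y/N. Fill the tally column from that item at sites that count by RDT.
- Leave the treatment item (item 7) unchanged.

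The cost is wording on the forms and formulas, since Box 2 already records the line results. The downside is that sites using combination tests may take slightly longer to reach 30 countable cases.

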## Annex 7. Survey case report form

Note: This is an example survey case report form. It may have to be amended to correspond with the RDTs used in the survey.

Note: Each survey form should be pre-labelled chronologically and there should be sufficient labels to place on RDTs, DBSs and plastic bags. Ideally, the form should be produced in duplicate.

Forms should be pre-filled to indicate the health centre and RDT-specific information, i.e. name, product code, target antigens, etc., and sections that are not applicable (N/A).

### To be completed prior to participant interview

1.	Barcode/patient ID	Place label									
2.	Health centre	Pre-entered for each health centre on printed form or combined with survey ID									
3.	Name of health worker/lab assistant										
4.	Date of visit	Day _____ Month _____ Year _____									
5.	Pre-entered for each health centre on printed form:  RDT 1 (must include HRP2 – national programme RDT)	 
 
 	Box 1	
 
 Control	Pf HRP2	
 
 + / -	+ / -	
 
 
Circle correct result in each box above.
 
Circle result of RDT:      1. Negative    2. P. falciparum
		Box 1	Control	Pf HRP2	+ / -	+ / -			
	Box 1										
Control	Pf HRP2										
+ / -	+ / -										
6.	RDT 2 (survey RDT)  a. Name: b. Product code: c. Lot number: d. Expiry date: e. Target antigens: 1. T1: 2. T2: 3. T3:	 
 
 	Box 2	
 
 Control	T2 Pf-LDH	T1 HRP2	
 
 + / -	+ / -	+ / -	
 
 
Circle correct result in each box above.
 
Circle result of RDT:      1. Negative    2. P. falciparum
		Box 2		Control	T2 Pf-LDH	T1 HRP2	+ / -	+ / -	+ / -
	Box 2										
Control	T2 Pf-LDH	T1 HRP2									
+ / -	+ / -	+ / -									
7.	a. Is RDT 1 positive for P. falciparum ? b. Is RDT 2 positive for P. falciparum ?	Y / N Y / N If YES to EITHER question, provide treatment.									

8.	DBS taken?	a. Y / N b. Consent for long term storage Y/N																				
9.	Microscopy	
  
 Microscopy	Positive/ Negative/ N/A	Species	Parasite count (parasites per microlitre)	Initials of microscopist	
   
 		Field health facility			
 
 		National laboratory cross-check (read 1)			
 
 		National laboratory cross-check (read 2)			
  
	Microscopy	Positive/ Negative/ N/A	Species	Parasite count (parasites per microlitre)	Initials of microscopist			Field health facility					National laboratory cross-check (read 1)					National laboratory cross-check (read 2)		
Microscopy	Positive/ Negative/ N/A	Species	Parasite count (parasites per microlitre)	Initials of microscopist																		
		Field health facility																				
		National laboratory cross-check (read 1)																				
		National laboratory cross-check (read 2)																				
To be obtained from each malaria suspect																						
10.	Age in years	_____																				
11.	Sex	a. M b. F																				
12.	Village where malaria suspect resides	_____ From pre-populated list if possible																				
13.	In the past two weeks, have you had a test for malaria?	a. No → Go to question 15 b. Yes																				
14.	What was the result of the test?	a. Positive b. Negative																				
15.	In the past two weeks, have you taken any medicine for malaria?	a. No → Go to question 17 b. Yes																				
16.	Antimalarial medicine taken	From pre-populated list d. ACT (whichever ACT is first-line drug in the country) e. Other ACTs (could be other names for first-line drug) f. Sulfadoxine/pyrimethamine g. Quinine h. Paracetamol (antipyretics available in country) i. Other _____																				
17.	Have you travelled to another locality of country in the past 30 days?	a. No → End b. Yes → Go to question 18																				
18.	Where did you travel?	a. Country _____ b. Region _____ c. District _____ d. City/Village _____ e. N/A																				

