  - *Note:* if budgetary or logistical constraints preclude the selection and inclusion of facilities using random sampling, a purposeful (or convenience) sample of facilities can be used. However, it should then be noted that domain-level estimates of *pfhrp2/3* gene deletions may not be statistically representative of the domain. If convenience sampling is conducted, efforts should be made to ensure that the sites are representative of the domain as a whole; otherwise, results will not have good external validity.
2. Survey procedures and analysis of data
  - Patients are triaged according to normal procedures. Any patient considered by the routine health provider, e.g. physician or nurse, to be a suspected malaria case according to national guidelines will be asked for consent/assent (Annexes 4 and 5).
    - Only consenting individuals will sign their name and be given a copy of the information sheet with their survey/sample ID in case they change their mind and wish to not participate in the future or wish to have samples removed from storage.

- Consenting patients will be asked a series of questions relevant to their illness and tested simultaneously according to the manufacturers' instructions for use by two separate diagnostics: the HRP2-based RDT used in the national control programme and either a Pf-LDH RDT or microscopy. A minimum of two DBSs will be collected on filter paper/protein saver cards.
- Non-consenting patients will receive routine care, and no record of their name or identity will appear on any survey documents. The blank non-consent form will be assigned a unique ID to allow for monitoring of the total number of consenting and non-consenting suspected malaria cases attending the facility on the survey tally sheet (Annex 6). All informed consent forms will be kept in a secure location under lock and key.
- The HRP2 and Pf-LDH RDTs will meet WHO procurement criteria and have approval for use by the Ministry of Health.

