  4. A minimum of two DBSs (50 µL per spot) on filter paper or protein saver card will be placed in a clean, dry and protected area and allowed to dry for 3–4 hours. Once dry, the filter paper/cards will be placed with the desiccant (from the RDT package) in a gas-impermeable plastic bag labelled with the survey ID if it is not stuck directly on the filter paper.
  5. Once the desired sample size of infected consenting individuals has been obtained at each facility, the survey case report forms and corresponding RDTs and DBSs should be compiled and sent to the central coordinating centre. No names or other unique identifying information should be contained on the forms, tally sheets, RDTs or DBSs. The only link between patient name and survey ID number should be on the consent form of the consenting individuals.
  6. Upon receipt of the forms, RDTs and DBSs, the survey team supervisor must review the RDT results section of the report form (Annex 7, section 5–7, S1 ), and determine which DBSs to prioritize for molecular +/- serological analysis (specifically, those that are HRP2 RDT negative and Pf-LDH or microscopy positive, and depending on resources, also a subset of HRP2 positive and negatives; see Annex 1) and which to discard.

Based on the number of discordant RDT or RDT-microscopy results, one can calculate the proportion of *P. falciparum* cases with suspected false-negative HRP2 RDT results (indicating potential *pfhrp2/3* gene deletions) in the health facility or domain (primary output indicator 2), using the formula below.

$$\text{Proportion of } P. \text{ falciparum} \text{ cases with suspected } pfhrp2/3 \text{ deletions} = \frac{\text{\# of } P. \text{ falciparum} \text{ cases with discordant RDT (HRP2- / Pf-LDH+) or discordant RDT-microscopy (HRP2- / microscopy+) results}}{\text{\# of confirmed } P. \text{ falciparum} \text{ cases (positive by Pf-LDH RDT or microscopy)}}$$

7. The DBSs (minimum of two) will be packaged and shipped for *P. falciparum* confirmatory testing and molecular +/- serological analysis for *pfhrp2/3* gene deletions to a WHO collaborating reference laboratory. Samples should be shipped under a material transfer agreement. Ideally, if more than two DBSs were collected, one DBS will remain in the survey country's reference laboratory at all times.

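### At facilities that use microscopy as the second test, the Annex 7 case report form neither prompts treatment nor flags discordance for HRP2-negative, microscopy-positive patients

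*Protocol*

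**What the plan says.** Section 5.6, step 2, has each consenting patient tested with "the HRP2-based RDT used in the national control programme and either a Pf-LDH RDT or microscopy". It expressly foresees sites that label one RDT and one slide, so some facilities will have no second RDT.

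The treatment rule includes microscopy. Step 7 of the data collection list in the project summary reads "Administer antimalarial therapy based on results from (either) RDT and/or microscopy, according to national guidelines". Section 5.6, step 2, refers the patient back to the clinician "for treatment in the case of positive test results on the primary or secondary RDT, or microscopy as per national guidelines".

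The discordance rule includes it too. Section 5.6, step 6, prioritizes "those that are HRP2 RDT negative and Pf-LDH or microscopy positive".

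In Annex 7, item 7 asks whether RDT 1 and RDT 2 are positive for *P. falciparum* and adds "If YES to EITHER question, provide treatment". The supervisor's line S1 asks whether box 1 is negative and box 2 positive, then states "If YES to part a and part b, the result is discordant". Both boxes hold RDT results. Microscopy has its own entry, item 9, with no instruction attached.

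Section 5.6 points users to the form twice. Step 2 tells the health worker to "record the results on the survey case report form (Annex 7, sections 5–7"), and step 6 says the supervisor "must review the RDT results section of the report form (Annex 7, section 5–7, S1 ), and determine which DBSs to prioritize".

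**The concern.** The form is what the health worker and the supervisor have in front of them. At a microscopy site its two decision lines are not connected to the second diagnostic test. A patient with a negative HRP2 RDT and a positive slide is the case the survey exists to find, yet the form gives no prompt to treat that patient and its discordance line does not pick up the sample.

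The stakes are, first, a missing treatment reminder for a confirmed malaria case and, second, a blood spot that may not be prioritized for molecular analysis. Step 6 of section 5.6 makes the second more than cosmetic: it directs the supervisor to S1 when deciding which blood spots to prioritize and which to discard. This is also a master protocol meant for use by many countries, so a gap in the template may be copied.

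**Working it through.** No published figure is involved, so the check sets the body-text rules beside the form's rules and runs every possible result through both.

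**Inputs**
- Treatment rule (project summary, data collection step 7; section 5.6, step 2): treat if the HRP2 RDT, the second RDT or microscopy is positive.
- Discordance rule (section 5.6, step 6): HRP2 RDT negative and either Pf-LDH or microscopy positive.
- Form treatment prompt (Annex 7, item 7): fires if 7a (RDT 1) or 7b (RDT 2) is YES.
- Form discordance line (Annex 7, S1): fires if box 1 is negative and box 2 is positive.
- Site type: HRP2 RDT plus microscopy, no RDT 2. The notes heading Annex 7 say inapplicable sections are pre-marked N/A. I take that to cover RDT 2 here, but answering 7b and S1 part b with N instead gives the same results.

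**All four result combinations at such a site**

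| HRP2 RDT | Microscopy | Body text: treat? | Item 7 prompt fires? | Body text: discordant? | S1 flags? |
|---|---|---|---|---|---|
| + | + | yes | yes (7a) | no | no |
| + | − | yes | yes (7a) | no | no |
| − | + | **yes** | **no** | **yes** | **no** |
| − | − | no positive result | no | no | no |

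**Results**
- Treatment prompt: fires for 2 of the 3 combinations that call for treatment.
- Discordance: S1 flags 0 of the 1 discordant combination. With no box 2 result, part b cannot be YES, so S1 returns no discordant samples at that facility however many there are.
- Cross-references: both places in section 5.6 that cite the form's result sections (2 of 2) stop at sections 5–7, or 5–7 and S1. Neither names item 9.

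**Comparison site.** Where the second test is a Pf-LDH RDT, 7b and S1 part b cover a Pf-LDH-positive result and the gap does not arise.

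The number of affected forms cannot be derived. The protocol gives neither the share of facilities that would use microscopy nor the expected share of discordant results.

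**The case against.** The strongest reply is that this is an editorial mismatch in a template. Annex 7 calls itself an example and says it may need amending to match the RDTs used; a one-RDT site differs from the printed two-RDT layout and would have to amend it. Section 5.6 requires each country to write its own operating procedure.

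The operative rules are correct in the body text, including in the very sentence of step 6 that cites S1. The output formulas also name the HRP2-negative, microscopy-positive pattern, so no estimate is redefined by S1. Item 7 says when to treat; it does not say to withhold treatment otherwise.

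A missed flag is recoverable. The Annex 6 tally sheet counts these patients by ID, section 5.8 requires consistency checks, and section 5.7.1 keeps RDTs and slides until the analysis is complete and discards unused blood spots only after results are reported.

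Most of this stands, and it is why the point is minor. It does not close the gap. The amendment note speaks of RDTs, not microscopy, and neither it nor the instruction to tailor procedures tells users to link item 9 to item 7 or S1. The form already carries a microscopy entry, so it is meant for such sites. The tally sheet confirms what the rule should be and that Annex 7 departs from it. The step 6 cross-reference is the weaker of the two, since it cites the RDT results section specifically; the one in step 2 covers slide sites and should include item 9.

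**Conclusion.** The point holds, at minor severity. Followed as printed at a microscopy site, Annex 7 misclassifies the HRP2-negative, microscopy-positive result as not discordant and gives no treatment prompt for it, contrary to section 5.6. The size is 1 of 3 treatable combinations without a prompt and 1 of 1 discordant combinations unflagged.

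This rests on the facility having no second RDT and on the form being used without local correction. It does not show that patients go untreated or that any survey output is biased: the correct rules stand elsewhere, and such samples can still be identified from the tally sheet and item 9.

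**What to change.** In Annex 7:
- Add *7c. Is microscopy (item 9) positive for P. falciparum? Y / N / NA*.
- Reword the prompt to *If YES to ANY question, provide treatment according to national guidelines*.
- Reword S1 part b to *Is box 2 (Pf-LDH) or field microscopy (item 9) positive for P. falciparum?*

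In section 5.6, extend the references to the form's result sections in steps 2 and 6 so that both include item 9.

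The cost is one added form line, two reworded lines and two corrected cross-references. Item 9 already captures the result, so no further test, procedure or sample is needed.
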